APPENDIX C. LIST OF PREFERRED TUMORS FOR THE ALL-TUMORS COHORT

Based on the bioinformatics study ([Section 1.2.1](#)) and the evaluation of KZR-261 in tumor xenograft models, the following tumor types are prioritized for inclusion in the All-Tumors cohort:

- Urothelial carcinoma
- Soft tissue sarcoma (except GIST)
- Head and neck carcinoma
- Small-cell lung cancer
- Hepatocellular carcinoma
- Pancreatic cancer

APPENDIX D. LIST OF SENSITIVE SUBSTRATES OF CYP3A4

The list below is available at <https://www.fda.gov/drugs/drug-interactions-labeling/drug-development-and-drug-interactions-table-substrates-inhibitors-and-inducers>. See also <https://drug-interactions.medicine.iu.edu/MainTable.aspx>.

Note: This list contains examples and is not intended to be exhaustive.

Category	Drug Names
Sensitive substrates of CYP3A	alfentanil, avanafil, buspirone, conivaptan, darifenacin, darunavir, ebastine, everolimus, ibrutinib, lomitapide, lovastatin, midazolam, naloxegol, nisoldipine, saquinavir, simvastatin, sirolimus, tacrolimus, tipranavir, triazolam, vardenafil budesonide, dasatinib, dronedarone, eletriptan, eplerenone, felodipine, indinavir, lurasidone, maraviroc, quetiapine, sildenafil, ticagrelor, tolvaptan

Signature Page for [REDACTED]

Approval Task	[REDACTED]
---------------	------------

[REDACTED]
2023 03:20:07 GMT+0000

Approval Task	[REDACTED]
---------------	------------

[REDACTED]
23 17:57:49 GMT+0000

Approval Task	[REDACTED]
---------------	------------

[REDACTED]
23 19:49:05 GMT+0000

Signature Page for [REDACTED]

## LIST OF ABBREVIATIONS

Abbreviation	Definition
AE	Adverse Event
aPTT	Activated Partial Thromboplastin Time
ATC	Anatomical Therapeutic Chemical
AUC	Area Under the Plasma Concentration-time Curve
CBR	Clinical Benefit Rate
CEA	Carcinoembryonic Antigen
CL	Clearance
C max	Maximum Plasma Concentration
CR	Complete Response
CT	Computed Tomography
D	De-Escalate to the Lower Dose
DLT	Dose-Limiting Toxicity
DOR	Duration of Response
DU	De-Escalate to the Lower Dose, Current Dose May Not Be Used Again Pending Advice of the Safety Review Committee
E	Escalate to the Next Higher Dose
ECG	Electrocardiogram
ECOG PS	Eastern Cooperative Oncology Performance Status
eCRF	Electronic Case Report Form
EI	Equivalence Interval
FBS	Fasting Blood Sugar
FIH	First-in-Human
ICH	International Conference on Harmonisation
IV	Intravenous
MAD	Maximum Administered Dose
mCRC	Metastatic Colorectal Carcinoma
mCRPC	Metastatic Castration-Resistant Prostate Cancer
MedDRA	Medical Dictionary for Regulatory Activities
MRI	Magnetic Resonance Imaging
MTD	Maximum Tolerated Dose
n	Number of Observations

Abbreviation	Definition
NCI CTCAE	National Cancer Institute Common Terminology for Adverse Events
ORR	Objective Response Rate
OS	Overall Survival
PAVA	Pool-Adjacent-Violators Algorithm
PCWG3	Prostate Cancer Working Group 3
PD	Progressive Disease
PFS	Progression-Free Survival
PK	Pharmacokinetics
PR	Partial Response
PSA	Prostate-specific Antigen
QTcF	QT Interval Corrected with Fridericia's Formula
RECIST	Response Evaluation Criteria in Solid Tumors
RP2D	Recommended Phase 2 dose
S	Stay at the same dose
SAE	Serious Adverse Event
SAP	Statistical Analysis Plan
SD	Stable Disease
[REDACTED]	[REDACTED]
SOC	System Organ Class
SRC	Safety Review Committee
$t_{1/2}$	Elimination Half-life
TEAE	Treatment-Emergent Adverse Event
VS	Vital Signs
$V_{ss}$	Volume of Distribution at Steady State
WHODrug	World Health Organization Drug Dictionary

## 1. INTRODUCTION

The purpose of this statistical analysis plan (SAP) is to describe in detail the planned analyses and reporting that may be conducted for protocol KZR-261-101, Version 5.0 dated 02 October 2023.

This SAP is being written with due consideration of the recommendations outlined in the most recent International Conference on Harmonisation (ICH) E9 Guideline entitled Guidance for Industry: Statistical Principles for Clinical Trials, the most recent ICH E9(R1) Addendum entitled Addendum on Estimands and Sensitivity Analysis in Clinical Trials to the Guideline on Statistical Principles for Clinical Trials, and the most recent ICH E3 Guideline, entitled Guidance for Industry: Structure and Content of Clinical Study Reports.

The statistical analysis methods presented in this document will supersede the statistical analysis methods described in the clinical protocol. If additional analyses are required to supplement the planned analyses described in this SAP, they may be completed and will be described in the clinical study report.

## 2. STUDY OBJECTIVES AND ENDPOINTS

### 2.1. Study Objectives

#### 2.1.1. Primary Objective for Part 1 (Dose Escalation)

- To evaluate the safety, tolerability, and PK of KZR-261 and identify the maximum tolerated dose (MTD) or maximum administered dose (MAD).

#### 2.1.2. Primary Objective for Parts 2A and 2B (Dose Expansion and Dose Optimization)

- To further characterize the safety profile of KZR-261 and identify the recommended Phase 2 dose (RP2D).

#### 2.1.3. Secondary Objectives

- To detect evidence of anti-tumor activity of KZR-261.
- To further characterize the PK of KZR-261 (Part 2A and 2B only).

#### 2.1.4. Exploratory Objectives

- To evaluate potential pharmacodynamic biomarkers in peripheral blood based on gene expression and proteomic changes.
- To explore and identify potential predictive biomarkers in tissue (including tumor) samples based on gene expression at baseline.
- To evaluate changes in potential predictive biomarkers during treatment.

## **2.2. Study Endpoints**

### **2.2.1. Primary Endpoints**

#### **2.2.1.1. Safety – Part 1**

Safety endpoints include the following:

- Incidence of dose-limiting toxicities (DLTs) during the DLT assessment period. DLTs will be assessed during Part 1 using pre-specified AE criteria detailed in [Protocol Section 3.2.3](#).
- Type, incidence, and severity of adverse events (AEs) and serious adverse events (SAEs), deaths, dose reductions, treatment interruptions and discontinuations due to toxicity, and changes from baseline in clinical laboratory parameters. Adverse events will be graded for severity per the National Cancer Institute Common Terminology Criteria for Adverse Events (NCI CTCAE) version 5.0.
- Changes from baseline in physical examination, ECG, and ocular examination findings.
- Changes from baseline in vital sign (VS) measurements and pulse oximetry.
- Identification of the MTD or MAD.

#### **2.2.1.2. Safety – Parts 2A and 2B**

Safety endpoints include the following:

- Type, incidence, and severity of AEs and SAEs, deaths, dose reductions, treatment interruptions and discontinuations due to toxicity, and changes from baseline in clinical laboratory parameters.
- Changes from baseline in physical examination, ECG, and ocular examination findings.
- Changes from baseline in VS measurements and pulse oximetry.
- Identification of the RP2D.

#### **2.2.1.3. Pharmacokinetic**

PK endpoints (if applicable) include the following:

- Plasma concentrations, including maximal plasma concentration ( $C_{max}$ ).
- Area under the plasma concentration-time curve (AUC).
- Elimination half-life ( $t_{1/2}$ ).
- Clearance (CL).
- Volume of distribution ( $V_d$ ).

## **2.2.2. Secondary Endpoints**

### **2.2.2.1. Anti-tumor Activity**

The anti-tumor activity of KZR-261 will be measured by the following:

- Objective response rate (ORR) defined as the rate of partial responses (PRs) plus complete responses (CRs) according to the revised Response Evaluation Criteria in Solid Tumors version 1.1 (RECIST v1.1) guidelines ([Eisenhauer et al., 2009](#)). Subjects with mCRPC will be assessed per Prostate Cancer Working Group 3 (PCWG3) guidelines ([Scher et al., 2016](#)).
- Clinical benefit rate (CBR), defined as the proportion of subjects achieving a best response of CR/PR or SD over at least 2 consecutive response assessment time points.
- Duration of response (DOR).
- Progression-free survival (PFS).
- Overall survival (OS).

## **2.2.3. Exploratory Endpoints**

### **2.2.3.1. Exploratory Biomarker Endpoints**

Exploratory endpoints include the following:

- Serum biomarker levels including cytokines and other circulating proteins.
- Whole blood gene expression changes.
- Protein profiling of peripheral blood mononuclear cells (PBMCs).
- Circulating tumor-associated proteins.
- Changes in circulating tumor DNA.
- Baseline gene and/or protein expression in pre- and on-treatment (post-Cycle 2) tumor biopsies to identify a potential predictive biomarker(s).

## **3. STUDY DESIGN AND PROCEDURES**

### **3.1. General Study Design**

This FIH, open-label, multicenter, Phase 1 study is designed to assess the safety and tolerability, preliminary anti-tumor activity, and the PK characteristics of KZR-261, as well as identify the RP2D. KZR-261 will be administered as a 30- to 60-minute IV infusion via a central line on Days 1, 8, and 15 of a 4-week (28-day) treatment cycle. (Doses may be held up to 7 days for resolution of non-DLT toxicity.) Eligible subjects will have locally advanced or metastatic solid malignancies and no available or approved therapies, or refused such therapies if available.

The study will be conducted in 2 parts: Part 1 (Dose Escalation) and Part 2 (Part 2A –Dose Expansion and Part 2B – Dose Optimization).

In Part 1, increasing doses of KZR-261 will be administered in an “i3+3” design to approximately 70 subjects to evaluate the safety and tolerability, PK, and pharmacodynamics of KZR-261, including identifying the MTD or MAD.

The Dose Expansion phase will commence following determination of the MTD/MAD and a review of the totality of safety data from Part 1. Part 2A will further characterize the safety profile of KZR-261 at the MTD or MAD and evaluate the anti-tumor activity of KZR-261 in subjects who have select malignancies. Up to 175 subjects may be enrolled in up to 4 tumor-specific cohorts (such as malignant melanoma [including uveal melanoma], mesothelioma, mCRPC, and mCRC) and 1 “All-Tumors” cohort. Additional or different tumor-specific cohorts may be investigated at the Sponsor’s discretion. Each tumor-specific cohort will enroll 15 subjects during Stage 1, expanding up to 35 subjects (Stage 2) as determined by a prespecified futility analysis and as long as the tumor type is not selected for investigation in Part 2B (see below). If futility is not rejected after Stage 1 (ie, prespecified criteria for futility are met), subsequent enrollment to that Part 2A cohort will cease. The All-Tumors cohort may enroll up to 35 biopsy-evaluable subjects.

Dose optimization in tumor-specific cohorts may be initiated at the Sponsor’s discretion based on the totality of data after the MTD/MAD has been determined. The Sponsor may choose to cease enrollment in the Part 2A tumor-specific cohort and initiate enrollment of that tumor type in Part 2B. Approximately 30 subjects within each tumor-specific cohort will be randomized in a 1:1 ratio to receive KZR-261 at the MTD/MAD or a lower clinically active dose of KZR-261 in Part 2B. Based on additional safety data from Part 2A, the Sponsor may convene an SRC meeting to determine whether a lower dose than the MTD/MAD as determined in Part 1 should be evaluated in Part 2B. Part 2B will further characterize the safety profile of KZR-261 to support determination of the RP2D and further evaluate the anti-tumor activity of KZR-261 in subjects with select malignancies. The number of tumor-specific cohorts to be investigated in Part 2B will be at the Sponsor’s discretion.

### **3.2. Schedule of Visits and Assessments**

The Schedule of Visits and Assessments are provided in [Appendix A](#) Schedule of Events for Cycles 1 & 2 and [Appendix B](#) Schedule of Events for Cycle 3+.

## **4. STUDY TREATMENTS**

KZR-261 is a small molecule protein secretion inhibitor formulated for clinical use as [REDACTED] KZR-261 for Injection is a lyophilized drug product that is supplied in vials delivering 75 mg of KZR-261 [REDACTED]. Each vial is reconstituted with sterile Water for Injection prior to administration. For all subjects, KZR-261 will be administered as an IV infusion via a central line on Days 1, 8, and 15 of a 4-week (28-day) treatment cycle. An IV infusion pump or syringe pump will be used for treatment of all subjects.

## 4.1. Dose Level Determination

### 4.1.1. Part 1 Dose Escalation Administration

The first cohort of subjects will be initiated with KZR-261 administered at  $1.8 \text{ mg/m}^2$ . Subjects will receive 3 doses in a 28-day cycle. Dose-escalation decisions for KZR-261 will be guided by the  $i3+3$  design with the targeted DLT rate  $pT=0.3$  and the equivalence interval (EI) = [0.25, 0.35]. The number of subjects that will be enrolled at each dose level for KZR-261 varies, with a minimum of 2 subjects per cohort, with a typical cohort size of 2-4, and with 6 to approximately 12 subjects dosed at potential MTD or MAD. Safety data from all subjects enrolled in each cohort will be reviewed to confirm occurrence of any DLTs experienced during the first cycle (DLT assessment period) to determine whether to expand the current cohort or to initiate enrollment into the next cohort as described in [Table 1](#).

The columns in [Table 1](#) represents the number of subjects enrolled at the dose, and the row represents the number of subjects experiencing any DLTs at the same dose.

**Table 1: Dose Escalation Decision Matrix for Part 1 Dose Escalation**

Number of Subjects with DLTs	Number of Subjects											
	1	2	3	4	5	6	7	8	9	10	11	12
0	E	E	E	E	E	E	E	E	E	E	E	E
1	S	S	S	S	E	E	E	E	E	E	E	E
2		DU*	D	D	S	S	S	S	E	E	E	E
3			DU	DU	D	D	D	D	S	S	S	S
4				DU	DU	DU	D	D	D	D	D	S
5					DU	DU	DU	DU	DU	D	D	D
6						DU	DU	DU	DU	DU	DU	D
7							DU	DU	DU	DU	DU	DU
8								DU	DU	DU	DU	DU
9									DU	DU	DU	DU
10										DU	DU	DU
11											DU	DU
12												DU

The dose-escalation decisions are as follows: E: Escalate to the next higher dose; S: Stay at the same dose; D: De-escalate to a lower dose; DU: De-escalate to a lower dose, the current dose may not be used again pending advice of the Safety Review Committee.

The initial dose cohort will receive KZR-261  $1.8 \text{ mg/m}^2$ . Subjects will receive 3 doses in a 28-day cycle. Dose administration is planned for Days 1, 8, and 15 of each cycle. Doses may be held up to 7 days for resolution of non-DLT toxicity.

A minimum of 2 subjects will be enrolled at each dose level of KZR-261. The number of subjects that will be enrolled at each dose level varies, with a typical cohort size of 2-4, and with 6 to approximately 12 subjects dosed at the MTD/MAD. Dose levels for cohorts and the percent increase in dose can be found in [Table 2](#).

**Table 2: Dose level by cohort**

Cohort	Dose Level (mg/m  )	Percent Increase from Previous Cohort's dose (%)
1	1.8	NA
2	3.6	100
3	7.2	100
4	12.0	67
5	18.0	50
6	27.0	50
7	40.0	50
8	60.0	50
9*	80.0	33

\*Additional dose cohort(s) may be needed to reach MTD/MAD

#### Definition of DLT

A DLT is defined as an AE or abnormal laboratory value that occurs during the first 28 days of treatment and meets the criteria listed below, unless it is assessed to be related to disease, disease progression, intercurrent illness, or concomitant medications.

Toxicities will be assessed by the Investigator using the NCI CTCAE Version 5.0. AEs that are not listed on the NCI CTCAE are to be assessed using the criteria in [Protocol Section 9.1.2](#). The attribution of an AE to KZR-261 is to be assessed by the Investigator using the criteria in [Protocol Section 9.1.3](#).

DLTs will be assessed in Cycle 1. Subjects who experience a DLT after the first, second, or third dose of KZR-261 will be counted as having a DLT but must be withdrawn from the study and will not be replaced. For subjects receiving study drug beyond Cycle 1, any late toxicities that occur after the DLT period (Cycle 1) will be assessed to determine the final MAD/RP2D to be carried forward in the dose expansion phase.

Subjects who do not experience a DLT in Part 1 Cycle 1 (Dose Escalation) must receive all of their scheduled doses (Days 1, 8, and 15) during the DLT assessment period with completed follow-up data available through 28 days of Cycle 1 to be eligible for DLT assessment (ie, DLT-assessable). Subjects in Part 1 Cycle 1 who miss a dose for non-AE-related reasons may be included in the DLT assessment period upon review by the Medical Monitor.

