Subjects who do not experience a DLT in Part 1, Cycle 1 (Dose Escalation) must receive all of their scheduled doses (Days 1, 8, and 15) with completed follow-up data available through 28 days of Cycle 1 to be eligible for DLT assessment. Subjects in Part 1, Cycle 1 who miss a dose for non-AE-related reasons will be replaced.

Both hematologic and non-hematologic DLTs include the following:

- Any AE that prevents the subject from receiving all planned doses during Cycle 1 (Doses may be held up to 7 days for resolution of non-DLT toxicity).
- Any AE that delays the initiation of Cycle 2 by >7 days because the AE has not resolved per criteria required for initiation of a new cycle ([Section 6.1.2](#) and [Section 6.1.4](#)).

Hematologic DLTs include the following:

- Grade 3 or 4 neutropenia (absolute neutrophil count [ANC] <1.0 × 10⁹/L) with a single temperature of >101°F (38.3°C), or microbiologically or radiographically documented infection.
- Grade 4 neutropenia (ANC <0.5 × 10⁹/L) in the absence of fever or infection lasting >7 consecutive days (complete blood count with differential must be measured every 2 to 3 days until recovery of ANC to ≤Grade 2).

- Grade 4 thrombocytopenia (platelet [PLT] count $<25 \times 10^9/L$) lasting >7 days (platelet counts must be measured every 2 to 3 days until recovery to \leq Grade 2 thrombocytopenia).
- Grade 3 or 4 thrombocytopenia (PLT count $<50 \times 10^9/L$) associated with clinically significant bleeding requiring platelet transfusion.

Non-hematologic DLTs include the following:

- Any non-hematologic AE \geq Grade 3, except the following:
 - Nausea, vomiting, diarrhea, electrolyte/metabolic abnormalities, constipation, fever, fatigue, or skin rash that resolves to \leq Grade 2 within 72 hours in the setting of optimal supportive care.
 - Grade 3 elevation in amylase or lipase without clinical or imaging manifestations of acute pancreatitis. In contrast, Grade 4 elevation in amylase or lipase and symptomatic Grade 3 lipase or amylase elevation are considered DLTs.
- Clinical signs and symptoms of acute pancreatitis.

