3.5. Safety Review Committee (Parts 1, 2A, and 2B)

The SRC will consist of the Medical Monitor (or designate), other Kezar representative(s), and participating Investigators. All Investigators who enroll subjects in the cohort under review will be consulted prior to the SRC meeting if they are unable to attend the scheduled meeting.

During Part 1, the committee will review safety data from the current cohort and previous cohorts before deciding on escalation to the next dose level. Dose escalation may occur only after the SRC has agreed ([Section 3.2.1.1](#)).

The totality of safety data from Part 1 will be reviewed prior to a declaration of the MTD/MAD. Available PK data may also be reviewed.

During Parts 2A and 2B, the SRC will periodically monitor safety data through the end of the study.

In Part 2, the study will be halted if there is one Grade 5 or two Grade 4 AEs in different subjects that are considered at least possibly related to KZR-261. Exceptions to the halting criteria include asymptomatic Grade 4 laboratory abnormalities (eg, neutropenia) that resolve either with or without routine supportive care measures and without sequelae. If this scenario occurs, a formal safety analysis will be conducted, and the findings will be submitted to the IND for the FDA to review prior to enrolling additional subjects.

A separate SRC Charter will describe the responsibilities of this committee for both dose escalation and dose expansion/dose optimization.

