### **6.3. DLT Evaluable Patients**

The DLT Evaluable Population consists of all subjects who either meet the following minimal exposure criteria and have sufficient safety evaluations without having a DLT, or have experienced a DLT during the DLT assessment period.

Subjects who do not experience a DLT in Part 1 Cycle 1 (Dose Escalation) must receive all of their scheduled doses (Days 1, 8, and 15) during the DLT assessment period with completed follow-up data available through 28 days of Cycle 1 to be DLT-assessable.

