## 12. MTD ESTIMATION AND DLT ANALYSES

In the dose escalation part,  $(x_d, n_d)$  will be observed for  $d=1, \dots, K$ , where  $d$  represents dose levels and  $K$  represents the total number of dose levels. Assuming  $n_d$  subjects have been treated at dose  $d$ , and  $x_d$  of them experienced DLTs, let  $x_d|p_d \sim \text{Bin}(n_d, p_d)$  and  $p_d \sim \text{Beta}(0.005, 0.005)$ . The posterior mean toxicity probability at dose  $d$  is estimated as,

$$\hat{p}_d = \frac{x_d + 0.005}{n_d + 0.01}$$

Isotonic regression will then be applied to the posterior mean DLT rates. Let  $\tilde{p}_d$  represent the isotonic-transformed posterior means for all the doses. The MTD will be the dose that satisfies  $\tilde{p}_d \leq 0.35$  and is closest to the target rate of 0.30. If multiple such doses satisfy the criteria, MTD will be the highest dose level that is  $\tilde{p}_d \leq 0.30$ . If no such doses, MTD will be the lowest dose that is  $\tilde{p}_d > 0.30$ .  $\tilde{p}_d$  is estimated using Pool-Adjacent-Violators Algorithm (PAVA), a solution to isotonic regression.

DLTs will be listed and summarized by MedDRA system organ class and preferred term. The DLT analysis set will be used for summaries.

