## **19. CHANGES FROM PROTOCOL-STATED ANALYSES**

There are no changes from the protocol-stated analyses.

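### SAP 4.1.1 lets DLT-free subjects who missed a Cycle 1 dose be counted at the Medical Monitor's discretion, against Protocol 3.2.3 and SAP 6.3, and this can only lower the observed DLT rate

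*SAP*

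**What the plan says.** The documents treat a Part 1 subject who has no DLT but missed a Cycle 1 dose for a reason other than an adverse event in different ways.

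- Protocol 3.2.3: "Subjects in Part 1, Cycle 1 who miss a dose for non-AE-related reasons will be replaced". The sentence before it makes all three doses and 28-day follow-up a condition of DLT assessment for a DLT-free subject.
- SAP 6.3: a DLT-free subject "must receive all of their scheduled doses (Days 1, 8, and 15) during the DLT assessment period". There is no exception. A subject with a DLT in the window is always evaluable.
- SAP 4.1.1, Definition of DLT: it repeats the all-doses condition and then adds "Subjects in Part 1 Cycle 1 who miss a dose for non-AE-related reasons may be included in the DLT assessment period upon review". The Medical Monitor carries out that review.

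Two further statements bear on which rule prevails. SAP 1 says: "The statistical analysis methods presented in this document will supersede the statistical analysis methods described in the clinical protocol". SAP 19 says: "There are no changes from the protocol-stated analyses".

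The SAP also describes the denominator in several ways. In SAP 4.1.1 a column of Table 1 "represents the number of subjects enrolled at the dose". SAP 12 counts subjects treated. The MTD definition in SAP 4.1.1 counts DLT-evaluable subjects. SAP 12 adds "The DLT analysis set will be used for summaries", a name that SAP 6 does not use.

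**The concern.** The SAP 4.1.1 sentence conflicts with the protocol, with SAP 6.3 and with the sentence before it. A programmer building the DLT set has two SAP rules and nothing to choose between them. SAP 1 gives the SAP's methods precedence, while SAP 19 says nothing has changed.

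The discretion has no stated criteria, and the trial is open-label, so whoever exercises it can already know the DLT count at that dose. It also works in one direction, because subjects with a DLT are counted regardless. Only DLT-free subjects with less than the planned exposure are left to admit.

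DLT incidence and identification of the MTD or MAD are primary endpoints of Part 1. Cohorts typically hold 2 to 4 subjects, with 6 to about 12 at the candidate MTD or MAD, so one subject can change a decision. Missed doses of this kind are foreseeable: Protocol 6.1.5 names scheduling and emergencies among the reasons.

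**Working it through.** **Inputs.** Table 1 (identical in protocol and SAP); equivalence interval 0.25 to 0.35 and target 0.30 (Protocol 10.5.1); MTD limit of 35% in at least 6 to 12 DLT-evaluable subjects (SAP 4.1.1). Let x be the number of subjects with DLTs and n the number counted.

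**Reproducing Table 1.** I compared x/n and (x−1)/n with the interval and marked DU where Pr(p > 0.30 | x, n) > 0.95. Protocol 10.5.1 names no prior. With an assumed Beta(1,1) prior, all 90 printed cells reproduce. The cell counts below use the printed table and need no prior.

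**Direction.** Against exclusion, the rate goes from x/n to x/(n+1), which is never higher and is strictly lower once x ≥ 1. At x = 0 the rate stays at zero, but the subject still adds to n. Against replacement at the same n, the admitted subject scores 0 and the replacement scores 0 or 1, so the rate with admission is never higher.

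**Comparison 1: count the subject instead of waiting for the replacement.** Moving from (x, n) to (x, n+1) for n = 1 to 11 gives 2 + 3 + … + 12 = 77 pairs. Ten change, none to a more cautious decision:

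| Change | Count | Cells |
|---|---|---|
| Stay to Escalate | 2 | 1/4 to 1/5; 2/8 to 2/9 |
| De-escalate to Stay | 3 | 2/4 to 2/5; 3/8 to 3/9; 4/11 to 4/12 |
| DU to D | 5 | 2/2 to 2/3; 3/4 to 3/5; 4/6 to 4/7; 5/9 to 5/10; 6/11 to 6/12 |

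The other 67 do not move. At the MTD limit, 2/5 (40.0%), 3/8 (37.5%) and 4/11 (36.4%) all become 33.3%. In the first case the added subject also brings n up to six.

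**Comparison 2: count the subject instead of a fully dosed replacement, same n.** If the replacement is DLT-free, nothing changes. If the replacement has a DLT, compare (x, n) with (x+1, n) for n = 2 to 12, again 77 pairs. The decision differs in 32: 11 Escalate versus Stay (for example 1/6 against 2/6), 11 Stay versus D or DU, and 10 D versus DU.

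**Probabilities.** With a replacement, X ~ Bin(n, p). With one under-dosed DLT-free subject counted, X ~ Bin(n−1, p) judged at the same n. The true DLT rate p in fully dosed subjects is an assumption.

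Example, n = 6 and p = 0.40, where Escalate means X ≤ 1:

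- Replacement: 0.6⁶ + 6 × 0.4 × 0.6⁵ = 0.047 + 0.187 = 0.233
- Admitted: 0.6⁵ + 5 × 0.4 × 0.6⁴ = 0.078 + 0.259 = 0.337

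| Event | n | Assumed p | Replacement | One admitted |
|---|---|---|---|---|
| Escalate (X = 0) | 3 | 40% | 22% | 36% |
| Escalate (X ≤ 1) | 6 | 20% | 66% | 74% |
| Escalate (X ≤ 1) | 6 | 30% | 42% | 53% |
| Escalate (X ≤ 1) | 6 | 40% | 23% | 34% |
| Escalate (X ≤ 1) | 6 | 50% | 11% | 19% |
| Escalate (X ≤ 2) | 12 | 40% | 8% | 12% |
| Rate ≤ 35% (X ≤ 2) | 6 | 40% | 54% | 68% |
| Rate ≤ 35% (X ≤ 3) | 9 | 40% | 48% | 59% |
| Rate ≤ 35% (X ≤ 4) | 12 | 40% | 44% | 53% |

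**The case against.** The case on the other side has five parts.

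- **Live escalation is governed elsewhere.** Replacing subjects is trial conduct under the protocol, and SAP 1 claims precedence only for statistical methods. Protocol 3.5 adds: "Dose escalation may occur only after the SRC has agreed". SAP 7.4 places the SAP's analyses after database lock. This stands as a condition: escalation decisions are affected only if the committee works from the SAP sentence.
- **The SAP already settles the MTD set.** The MTD is defined on DLT-evaluable subjects, SAP 6.3 defines them without exception, and the sentence speaks of the assessment period, not the population. This stands in part. However, the sentence directly follows the definition of a DLT-assessable subject, so it reads most naturally as an exception to it, and SAP 12 counts subjects treated.
- **The table assumes that one subject has been admitted.** This is correct. SAP 11.1 expects no compliance problem because dosing is in clinic. Averaged over assumed missed-dose rates, with DLT rates of 40% in fully dosed and 27% in under-dosed subjects and every such subject admitted, the n = 6 Escalate probabilities (replacement versus admission) are 22% vs 24% at a 5% miss rate, 21% vs 25% at 10% and 18% vs 28% at 20%. The average effect is smaller, but the direction is the same.
- **Replacement is itself biased.** It keeps a partly dosed subject only if a DLT occurs. On the same assumptions with 10% missing a dose, the expected rate is 41.8% with replacement and 38.7% with admission, against 40% under full dosing. The one-way claim is therefore relative to replacement or exclusion, not to the true rate. The upward bias is in the cautious direction.
- **The 35% figures test one dose.** SAP 12 applies isotonic regression across doses and picks the one closest to 0.30. The figures show movement across the limit, not the final selection.

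**Conclusion.** The concern holds. SAP 4.1.1 gives an undeclared discretion, without criteria, that contradicts Protocol 3.2.3, SAP 6.3 and its own preceding sentence. Compared with replacing or excluding these subjects, it can leave the observed DLT rate unchanged or lower it, but cannot raise it. That direction follows from the definitions and needs no assumption.

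The size does rest on assumptions. With one admitted subject and a true rate of 40%, the chance of an Escalate cell rises by 4 to 14 percentage points over the cohort sizes shown, and the chance of meeting the 35% limit by 9 to 14 points. How often such subjects arise is not stated. The MTD estimate is exposed only if SAP 4.1.1 is read as overriding SAP 6.3, which the mixed denominators leave open. It should be fixed because it touches a primary endpoint and the repair is small.

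**What to change.** Reconcile Protocol 3.2.3, SAP 4.1.1 and SAP 6.3 to one DLT-evaluable set that feeds Table 1, the DLT summaries and the isotonic MTD estimate.

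1. Delete the sentence in SAP 4.1.1 that allows inclusion, and refer to SAP 6.3. These subjects stay in the Safety Population.
2. State in SAP 4.1.1 and SAP 12 that n is the DLT Evaluable Population, and use that name in place of the undefined one in SAP 12.
3. If the sponsor wants an exception, declare it in SAP 19 with criteria fixed in advance, and report the MTD estimate with and without the subjects concerned.

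The cost is one deleted sentence and two clarified denominators in the SAP. Protocol 3.2.1 (subjects enrolled) and 10.5.1 (subjects treated) use the same loose terms and could be aligned at the next amendment. The protocol already plans the replacements. No dose or clinical rule changes.
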